*These cutoff scores are consistent with the mental health alerts through Project SafeSchools. If a caregiver reports the youth to be at risk of mental distress, the youth will proceed to be screened based on self-report.

Please note that it is not a requirement that both the adult caregiver and their child have elevated mental health risk in order to be eligible to participate in this study. The intervention and all data collection are done at an individual level not on a dyad basis.

B. Exclusion Criteria:

Inability to cognitively complete interventions and assessments.

About the White Mountain Apache Tribe

The White Mountain Apache Tribe (WMAT) resides in eastern Arizona on the Fort Apache Indian Reservation. There are approximately 15,500 tribal members who live within the 1.6-million-acre land base. JHCAIH has a 30+ year track record working with the WMAT to build frugal public health solutions that can scale to other low-income, underserved communities.

A reflection of the dire needs of many reservation-based populations, there is significant poverty among the White Mountain Apache: 61% of the population over 16 years old are either "Not in Labor Force" or unemployed. The median household income is \$14,496, and 87% live below the federal poverty line. Fewer than half of Apaches older than 25 years of age have graduated high school, and 4-year college graduation, while increasing, remains less than 10%. Apache youth have extreme needs. Over half (54%) of Apache tribal members are below age 25, compared to approximately 35% of the overall U.S. population. Challenges brought on by historical trauma and related environmental risks significantly impact Apache youth's life course. Their psychosocial, educational and health disparities include high rates of school dropout, unintended teen pregnancy, and premature death from suicide, motor vehicle deaths, and substance misuse.

About the Navajo Nation

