If a potential participant is interested, depending on preference, consent/assent will be administered during the same visit or scheduled for another day. If the person is not interested, they will be thanked for their time and continue to receive support for their mental health concerns and safety and continue to be enrolled in the Project SafeSchools cohort study. Study staff will document their decision in REDCap, and they will not be approached again about participation in +CiM/HSP.

As part of the consent process, individuals will consent to accessing their data collected in the Project SafeSchools cohort study. Eligibility screening for the +CiM/HSP study will occur after consent to participate and as part of the baseline assessment (Figure 1). An individual must score at or above the cut-off score on any of the mental health screening tools (see Table 2) to be included. If the person is determined to be ineligible after this screening, they will be notified by the study staff and informed that this ineligibility for +CiM/HSP study will in no way affect their participation in the Project SafeSchools study. If the participant is eligible for +CiM/HSP, they will continue with the rest of the assessment and other study activities.

This study is an individual intervention, not based on dyads. Only those caregivers and youth with elevated mental health scores at screening will participate. A parent/caregiver and youth can participate without the other being enrolled.

d. Whether you will obtain a signature from the participant or will use an oral consent process:

We will use an online or oral consent/permission/assent process due to COVID and to protect privacy.

e. Whether you will obtain a legally authorized representative's signature for adults lacking capacity:

N/A

f. If children are included in the study, if and how you will obtain assent from them:

Assent will be obtained following parent permission to be involved in the study.

g. If children are included in the study, how you will obtain permission for them to participate from their parent, legal guardian, or other legal authority (if child is in foster care or under government supervision). If any of the children are "wards of the state", additional regulatory requirements will apply:

Parent permission will be obtained orally either over the phone or in-person prior to youth assent.

h. If you are seeking a waiver of informed consent or assent, the justification for this request:

N/A

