A username and password are required to access the REDCap system. Study staff will launch the assessments on a tablet or, if preferred, via a link to the survey that participants can access from their phone or personal computer/tablet. If needed forms can be printed and provided on paper, but data must be entered into REDCap as soon as the staff member has it back at the office. Tablets will be synced daily with REDCap using a secure Wi-Fi connection available at the study site. For the assessments completed via phone, staff will read the questions to the participant. Study staff are trained to provide additional information to clarify questions as necessary. If in-person, the study staff member will provide the tablet to the participant so that they can complete the assessment via selfreport. If done on paper, the study staff will provide the paper packet. They will be available if questions should arise. Data collected through REDCap is automatically stored on a Johns Hopkins HIPAA compliant, secure server. Direct data entry into REDCap eliminates the need for separate data entry and coding. Any data that is collected via hard copy will be entered into REDCap. Once entered into REDCap, for any participant who scores above pre-established cutoffs on mental health instruments or indicates suicide risk (see Safety Monitoring section), a notification will appear on the tablet to the interviewer to proceed with safety procedures. An additional email alert to the site supervisor, PI and study coordinator will also occur when the data is uploaded to the server to promote communication and allow for timely follow-up. Data will be downloaded from REDCap as a complete database into de-identified Excel and Stata files that will be stored on Johns Hopkins' HIPAA compliant, secure server. Data will be retained until the end of study analysis or three years after the final participants exit the program, whichever comes first.

Each assessment timepoint include the following scales or items by type of respondent:

Table 5. Parent/Caregiver Time points and Measures

Domain	Instrument	Items	Baseline/ Screener	30 Days	90 Days	Included in PSS secondary data analysis
Adult Self-Report						
	Menta	l Health	Outcome Don	nains		
General Distress	Kessler	11	Χ	Χ	X	X
Depression Symptoms	CESDR-10	10	X	Х	X	X
Anxiety Symptoms	PROMIS	8	Х	Х	Х	X
	Intermediary Ou	ıtcome [Domains/Prog	ram Fee	dback	

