Participants in this study have been identified as being at risk for more severe mental health concerns including anxiety, depression, and suicidal ideation or past behavior. As such, study participants will be allowed and encouraged to access any available outside mental or behavioral health care. All study staff are knowledgeable about resources in the community that are available for any medical, mental, or behavioral health need. As part of our other studies, we have compiled a list of these resources in each site, and regularly update this resource list to ensure accurate information. There are several assessments in the assessment instruments we are using battery that have validated cutoff scores indicating the individual might be at risk for more severe mental health concerns. If an adult participant responds in a way that meets the cutoff score for themselves or indicates through their responses that their youth meets the cutoff score, the participant will receive a referral to local mental and behavioral health services and be encouraged to contact those services as soon as possible. If a participant asks for or requires additional outside care, study staff will work with their site manager and Pls (if necessary) to provide information to the participant on how to access that care.

VI. Data Custody, Management, Security, and Confidentiality Protections: Data security and management plans must meet institutional standards. If you need assistance, contact [contact].

Investigators are responsible for ensuring the security of data from the time of collection, through any transfers from one system to another, analysis, sharing, storage, and ultimate archiving and disposal. The questions below seek to elicit your plans for these protections. Feel free to add information.

1.	Dat	a Sources: Identify the source(s) of data.
	\boxtimes	Participant/Parent-Guardian/Legally Authorized Representative
		JHM Medical Records (from Epic)
		Note for JHM Data Users Only: Please complete the Data Trust Risk Tiers Calculator available
		on the Applications and Forms page on the JHSPH IRB website: https://tinyurl.com/2p96md3s and
		upload a copy of the documents to the "Miscellaneous- Other" section of your PHIRST application.
		In addition, review the Data Protection Attestation for Research and/or Healthcare Operations
		at: https://tinyurl.com/yszfkuur and certify your attestation of compliance to those requirements.

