- 3. **Informed consent/assent.** We will provide potential respondents a clear opportunity to understand the study objectives and procedures, to assess study risks and benefits, and, verbally, to give or decline consent freely and without pressure or penalty.
- 4. Mental health referrals. The assessments for the proposed study are the same as what is currently being used in the associated Project SafeSchools cohort study for adults and caregiver reports on youth. As such, we will continue to use the mental health referral procedures that have already been approved for that study. Briefly, if adult participants respond on the CESDR-10, or PROMIS anxiety measure (parent/caregiver participants) in a way that meets or exceeds the cutoff score or indicate their child (parent/caregiver participants) meets the standard cutoffs on the SDQ, or SCARED, will receive a referral to local mental health services on the Reservation and be encouraged to contact these

IRB #00020570 +CiM/HSP research plan v7 14Nov2022

Pls: [name] (Faculty PI) & [name] (Navajo Community PI)

services. Similarly, if any youth self-reports on the CESDR-10, SDQ or SCARED we will use the same referral processes. We have strong relationships with local services in each site, which include services for both adults and youth and including ongoing collaboration with mental health and suicide response teams on both the Fort Apache Indian Reservation and Navajo Nation. If a participant asks or requires urgent mental health care, study staff will inform the site manager and PIs (if necessary) and they will follow up with the study participant to further assess and provide information to the participant on how to access appropriate care. All study team members will have completed Psychological First Aid training.

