- 5. Suicide Risk Plan. An imminent risk procedure was developed by JHU for previous studies to ensure triage and access to emergency care for suicidal individuals. Risk will be gauged by immediately scoring the suicide-related questions. Questions from the CESDR-10 that indicate recent suicide ideation (i.e., in the last two weeks) for adults and youth will be identified and flagged in REDCap and an automatic alert setting for these questions will automatically alert senior members of the study team. Study team members have all received Applied Suicide Intervention Skills Training (ASIST) and can respond in crisis situations. If the study team receives an alert for suicidal ideation based on a participant completing the survey instruments online (adults only; youth are not allowed to complete surveys online) after working hours, a text will be sent to them that contains the National Suicide Prevention hotline number and crisis text line. Study staff will follow up with them within 24 hours to provide additional support and resources. To make it possible to send the text message, we will enable Twilio integration in REDcap. See the 'Miscellaneous Documents' for the details of this Suicide Risk Safety Procedures.
- 6. **Staff training and familiarity with local context.** We have attempted to minimize these risks by employing Native paraprofessionals who are trained in active listening, problem-solving, maintaining confidentiality, assessing worsening of symptoms, providing support, and other relevant procedures, including basic relaxation techniques to ensure each participant's comfort and well-being. If any participant becomes distressed during the surveys or interviews, a break will be provided, or the survey/interview will be stopped, and the research staff will work with the participant to reduce the participant's distress using basic relaxation techniques. If the participant's distress is not able to be addressed by these approaches, the Research Program Assistants will ask if the participant wishes to address the distress in another manner and will facilitate the participant's request when possible. In addition, Research staff can enlist the site supervisors at each site to talk with the participant via phone and facilitate referrals if necessary.
- 7. **Data Storage and Protection.** No unique identifiers will be collected in data collection forms or handwritten notes

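### The automated REDCap alert is worded to fire above the symptom cutoffs, while the plan's eligibility and referral rules count a score at the cutoff

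*Combined protocol and SAP*

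**What the plan says.** Section V.C.1.iii (Assessments) describes an automated alert once data are in REDCap. It fires "for any participant who scores above pre-established cutoffs on mental health instruments or indicates suicide risk". It has two outputs. One is a tablet notice telling the interviewer to start the safety procedures. The other goes to senior staff: "An additional email alert to the site supervisor, PI and study coordinator will also occur when the data is uploaded to the server". The same section lets assessments be completed "via a link to the survey that participants can access from their phone or personal computer/tablet". Section VII.B.5 restricts online completion to adults.

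Four other places set the threshold for the same instruments:

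- Table 2 (Section IV.A) gives each symptom cutoff as a value with a plus sign, such as 8+ for CESDR-10 and 17+ for PROMIS. Its footnote on the caregiver-report rows adds: "These cutoff scores are consistent with the mental health alerts through Project SafeSchools".
- Section V.B.1.c (eligibility): "An individual must score at or above the cut-off score on any of the mental health screening tools".
- Section V.C.5.F.f (referral to outside care) applies when an adult "responds in a way that meets the cutoff score for themselves or indicates through their responses that their youth meets the cutoff score".
- Section VII.B.4 (mental health referrals) applies "if adult participants respond on the CESDR-10, or PROMIS anxiety measure (parent/caregiver participants) in a way that meets or exceeds the cutoff score". It then covers caregiver reports on the SDQ and SCARED, and youth self-report on the CESDR-10, SDQ and SCARED.

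**The concern.** The alert is the automated step that brings a high score to staff attention, so its threshold should match the one at which the plan says a referral is due. As worded, it does not. A participant exactly at a symptom cutoff is high risk under Table 2 and due a referral, but is not above the cutoff. A programmer building the alert from Section V.C.1.iii alone would code a strict inequality.

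At baseline this matters little, because the at-or-above eligibility rule already identifies these people. At 30 and 90 days nobody is being screened in. An adult who answers by link has no interviewer to see a tablet notice, so the email is the score-based prompt that Section V.C.1.iii leaves. The two check-ins do not fill the gap. Section V.C.1.i places them a couple of days after the coping-plan visit and in the following week, and Table 4 shows them in the first two quarters of month 1. The 30-day survey has a window of ±10 days, so it opens at day 20.

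**Working it through.** The plan states no figure on this point, so there is none to reproduce. The check compares the wording and then counts the scores that each wording captures.

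**Operators side by side**

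| Place | Purpose | Is a score equal to the cutoff counted? |
|---|---|---|
| Table 2, Section IV.A | High-risk definition | Yes (N+) |
| Section V.B.1.c | Eligibility | Yes (at or above) |
| Section V.C.5.F.f | Referral | Yes (meets) |
| Section VII.B.4 | Referral | Yes (meets or exceeds) |
| Section V.C.1.iii | Tablet and email alert | No, read literally (above) |

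**Scores captured.** For integer scores with maximum M and cutoff c, the number of values at or above the cutoff is M − c + 1, and the number strictly above is M − c. Ranges and cutoffs are from Table 2.

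| Symptom row | Range | c | At or above | Above | Value lost | Adult can complete by link? |
|---|---|---|---|---|---|---|
| Adult Kessler | 0–24 | 13 | 12 | 11 | 13 | Yes |
| Adult CESDR-10 | 0–30 | 8 | 23 | 22 | 8 | Yes |
| Adult PROMIS | 8–40 | 17 | 24 | 23 | 17 | Yes |
| Caregiver SDQ | 0–10 | 5 | 6 | 5 | 5 | Yes |
| Caregiver SCARED | 0–82 | 25 | 58 | 57 | 25 | Yes |
| Youth CESDR-10 | 0–30 | 8 | 23 | 22 | 8 | No |
| Youth SDQ | 0–10 | 6 | 5 | 4 | 6 | No |
| Youth SCARED | 0–82 | 25 | 58 | 57 | 25 | No |

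One high-risk value is lost in each of 8 rows, and 5 of the 8 can be completed by an adult by link.

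**Rows left out.** Table 2 has 11 rows. The other 3 concern suicidal ideation: the CESDR-10 item for adults, the same item for youth, and the caregiver report. The alert sentence has a separate limb for a participant who indicates suicide risk, and that limb needs no score above a cutoff. The operator conflict therefore does not decide what happens for these rows.

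**The case against.** The strongest reply is that *above* is loose drafting. The alert sentence sets no threshold of its own. It points to cutoffs fixed elsewhere, and those are inclusive everywhere they appear. Nothing in the file shows REDCap programmed with a strict inequality. This is probably right about intent. The conflict in the text remains, however, and this sentence is the one that describes the automated trigger.

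A second reply is that referral does not hang on the alert. Sections V.C.5.F.f and VII.B.4 make a person at the cutoff due a referral however the alert is read, and neither says that the alert must fire first. Section X.C.1 also provides a community resource list with each assessment visit, although delivery with a link survey is not spelled out. This reply stands. A reader might infer that people at a cutoff would be left without referral, and the documents do not support that.

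A reader might also infer that a caregiver's report of a child's suicidal ideation triggers nothing. Its cutoff of 4 is the top of a 0–4 scale, so no score can exceed it. Section VII.B.4 names only the SDQ and SCARED for caregiver report, and the automatic flag in Section VII.B.5 names only CESDR-10 items: "Questions from the CESDR-10 that indicate recent suicide ideation (i.e., in the last two weeks) for adults and youth will be identified and flagged". The inference fails because it applies the symptom limb of the alert to a suicide item. General wording covers this answer in four places: the suicide-risk limb in Section V.C.1.iii, the youth-cutoff referral in Section V.C.5.F.f, the immediate scoring of suicide-related items in Section VII.B.5, and the notification after any assessment in Section X.C.1. Section VII.B.4 also presents itself as a summary, and the detailed Suicide Risk Safety Procedures are in a separate document that is not in the file. Naming the item would be clearer, but its absence from the two lists is not an error.

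**Conclusion.** The inconsistency is real and minor. The stated alert threshold excludes a score at the cutoff, and the plan's definition of high risk, its eligibility rule and its referral rules all include it. Its size is one value in each of 8 symptom rows. The practical exposure is mainly the 5 adult-completed rows at 30 and 90 days, when the survey is done by link.

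No number of affected participants can be derived. It is tempting to combine the planned 75 adults with the standard deviations in Table 1, but those are baseline values. The documents give no follow-up means and no share of adults answering by link. They also do not say how often a person at one cutoff would be above another and so fire the alert anyway.

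The conclusion rests on a literal reading of the word and on taking the alert to cover caregiver reports as well as self-reports. Confidence is high for the wording only. How the alert actually behaves depends on the REDCap conditions, which are not in the file. Nothing here affects randomisation, endpoints, power or analysis.

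**What to change.** In Section V.C.1.iii, replace *above* with *at or above*, and confirm that every REDCap alert condition uses ≥ with the Table 2 value. One cutoff should be settled at the same time, as a separate question: Table 2 gives 6+ for the youth self-report SDQ, while the instrument description in Section V.C.1.iii.c gives 5+.

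As an optional clarification, name caregiver-reported youth ideation and self-harm in the referral list of Section VII.B.4 and in the automatic flag of Section VII.B.5, and check that the Suicide Risk Safety Procedures agree.

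The required change is one phrase and a check of the alert settings. The optional one adds one item to a list and one to a flag. Neither needs new data. The running cost is slightly more alerts for staff to handle.
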